#### **6.3.1.3. Missing Cellulite Onset Date**

Missing cellulite onset days will be imputed with the first day of the month and missing onset month will be imputed with January.

If the onset date is indicated as completely unknown but starting less than 5 years ago, the onset date will be imputed as the informed consent date minus 5 years.

If the onset date is indicated as completely unknown but starting more than 5 years ago, the onset date will not be imputed.

Missing cellulite medication/treatment end days will be imputed with the last day of the month and missing end months will be imputed with December, except if the end year is equal to the date of injection year and then the cellulite medication/treatment end date will be imputed with the first injection date.

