**Table 2: Schedule of Activities (Continued)**

Activities	Screening	Treatment Phase a						Follow-up
	(Day -28 to Day -1)	Day 1 Visit 1	Day 28 (±3 day) Visit 2	Day 56 (±3 days) Visit 3	Day 84 (±3 days) Visit 4	Day 112 (±3 days) Visit 5	Day 140 (±3 days) Visit 6	Day 180 End of Study/ Early Termination Visit (±10 days)
[REDACTED]		X						X
Assignment of treatment area (buttocks or thighs)	X							
Confirm eligibility		X						
Randomize treatment arm		X						
Digital photography k		X	X	X	X	X	X	X
Study intervention administration		X l	X l	X l	X l	X l	X l	
Prior/Concomitant medications/ procedures	Collect throughout the study							
AEs	Collect throughout the study							

a During unscheduled visits the investigator or designee may perform any study procedure deemed clinically necessary (eg, vital signs, clinical laboratory assessments, pregnancy test, etc).

b Performed prior to any study-required assessments.

c Should be reassessed and verified prior to dosing.

d For these eligibility confirmation photographs the subject will be standing in a consistent, standardized relaxed standing pose (ie, standing position with relaxed gluteus muscles) and will be wearing a standardized photographic garment. Specific instructions for taking the eligibility confirmation photographs as well as for providing them to, and receiving confirmation (or lack thereof) from, the sponsor designated reviewer will be provided in the Study Operations Manual.

e On treatment phase visit days (Days 1, 28, 56, 84, 112, and 140) vital signs will be taken up to 4 hours prior to dosing and at 15 minutes and 30 minutes after dosing (body temperature is not required at the 15 minute postdose time point).

f These assessments, which will be based on digital photographs, are performed separately for each of 2 treatment areas and must be completed before study intervention administration on those visits. If at a treatment visit, use photographs taken before marking treatment area.

g [REDACTED]

h Subjects with Hexsel CSS Subsection D score greater than 3 at screening are excluded. A score greater than 3 is defined as an appearance significantly worse than exhibited in the Hexsel CSS Subsection D severe (score = 3) image.

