**Table 19: Derived Variables and Definition**

Variable	Definition
Age Group	18 – <35 years 5 – <45 years 45 – 55 years
Height (cm)	If height is recorded in inches, then height is equal to the recorded value multiplied by 2.54 and then rounded to 1 decimal place.
Weight (kg)	If weight is recorded in pounds, then weight is equal to the recorded value multiplied by 0.454 and then rounded to 1 decimal place.
Body Mass Index (BMI)	BMI will be computed using height measured at screening and body weight measured at respective visits as, $BMI (kg/m^2) = Weight (kg) / Height (m)^2$
Relative Day	The day of first injection of study drug will be considered as relative Day 1.
Study Day (for assessment on or after Day 1)	Study Day will be computed as: Date of Assessment – Date of Day 1 + 1
Study Day (for assessment before Day 1)	Study Day will be computed as: Date of Assessment – Date of Day 1
Baseline	Baseline is defined as the last non-missing measurement/assessment prior to the first dose of study drug. For clinical laboratories this will be the screening value. The assessments made in unscheduled visits will be considered in calculation of baseline, if the unscheduled assessment is the closest value preceding the first dose of study drug.
Baseline for Vital Signs on Injection Days	For vital signs on injection days, the baseline value will be the vital sign measure immediately prior to the first dose of study drug.
Change from baseline	Change from baseline will be derived as: post baseline visit/time point value – the baseline value.
Last (analysis)	Last is defined as the last non-missing measurement/assessment post the first dose of study drug.
Last Date in Study	Last date in study is defined as: 
 
• The date of Day 180 Visit if the subject completes the study.
 
• The date of ET visit if the subject is terminated early from study at a non-scheduled visit.
 
• The date of the latest scheduled visit if the subject is terminated early from study at a scheduled visit or lost to follow-up.
 

Age (Years) at cellulite Onset	(Date of cellulite symptoms reported – Date of Birth)/365.25. See Section 6.3.1.3 for handling of partial or unknown Cellulite symptom onset dates.
Time (Years) since last cellulite treatment	(Date of informed consent – Date of most recent cellulite treatment)/365.25. See Section 6.3.1.3 for handling of partial or unknown treatment dates.

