### **7.5. Cellulite History**

Cellulite history will be summarized by treatment regimen and overall using frequency counts and percentages which will include:

- Age (years) at cellulite symptom onset (summarized descriptively).
- Prior treatments for cellulite including liposuction, laser, massage, radiofrequency, drug, mesotherapy, cream, other, or none. Subjects can report more than 1 prior cellulite treatment.
- Number of prior cellulite treatments (0, 1, 2, or ≥3).
- Time (years) since most recent cellulite treatment (summarized descriptively).

Refer to [Table 19](#) for computation of “age at cellulite onset” and “time since last cellulite treatment.” Cellulite history will be listed.

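### For partial end dates in the injection year, the SAP imputes a cellulite-treatment end date that falls after consent, so time since last cellulite treatment comes out negative

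*SAP*

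**What the plan says.** SAP 6.3.1.3 has a default and an exception for incomplete treatment end dates. The default is: "Missing cellulite medication/treatment end days will be imputed with the last day of the month and missing end months will be imputed with December". The exception follows in the same sentence, "except if the end year is equal to the date of injection year", and in that case "the cellulite medication/treatment end date will be imputed with the first injection date". Neither branch limits the imputed date to consent or to the Screening Visit.

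SAP Table 19 defines time since last cellulite treatment by the formula "Date of informed consent – Date of most recent cellulite treatment)/365.25", that is, the difference in days expressed in years. It adds: "See Section 6.3.1.3 for handling of partial or unknown treatment dates". Table 19 does not say whether the treatment date is a start or an end date. The end-date rule is the only treatment-date rule in the section it points to, so that rule governs.

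Three other places fix the order of events:
- SAP Table 2 puts informed consent in the screening column, Day -28 to Day -1, with the note "Performed prior to any study-required assessments".
- Table 19 states: "The day of first injection of study drug will be considered as relative Day 1".
- SAP 4.5 counts a treatment as prior when it is reported before the Screening Visit.

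SAP 7.5 summarizes the variable descriptively, by treatment regimen and overall.

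**The concern.** The variable is counted back from consent, but in the exception branch the treatment is dated to an event that comes after consent. A time since a past treatment cannot be below zero, so the baseline table could show an impossible minimum and a shifted mean. With 16 subjects planned per regimen, a few such records would be visible. The imputed date also conflicts with SAP 4.5, because a treatment reported as prior to screening is given an end date on the day of first dosing. The same section of the SAP anchors an unknown onset date to informed consent, so the section uses two different reference points.

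A second problem is the wording. The exception follows both the missing-day clause and the missing-month clause and is not restricted to either. On its face it applies when the month is known and only the day is missing, and so replaces recorded information with the injection date.

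**Working it through.** The plan states no figure for this variable, so there is nothing to reproduce. The check applies the rule and the formula to dates.

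**Inputs**
- Consent-to-injection gap *g*: 1 to 28 days (SAP Table 2, screening Day -28 to Day -1; Protocol 5.4, up to 28 days). Under the Table 19 study-day formula for assessments before Day 1, Day -1 is one day before the first injection and Day -28 is 28 days before.
- Formula: (consent date - treatment date) / 365.25 (SAP Table 19).
- Imputed treatment date in the exception branch: first injection date (SAP 6.3.1.3).
- The calendar dates in the cases below are assumptions, chosen to fall near the protocol's estimated study period.

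**1. Exception branch, any dates.** The treatment date equals consent + *g*, so the result is -*g*/365.25.
- *g* = 1: -1/365.25 = -0.003 years.
- *g* = 21: -21/365.25 = -0.057 years.
- *g* = 28: -28/365.25 = -0.077 years.

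The sign depends only on *g* being at least 1. Zero cannot occur under the schedule.

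**2. Year-only date in the injection year.** End date 2020, consent 24 Nov 2020, injection 15 Dec 2020. The rule gives 15 Dec 2020. Consent minus that date is -21 days, or -0.057 years. This holds on any reading of the exception.

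**3. Known month, day missing.** End date March 2020, same consent and injection dates.
- Literal reading: March is replaced by 15 Dec 2020, giving -21 days = -0.057 years.
- Month kept: 31 Mar 2020, giving 238 days = 238/365.25 = +0.652 years.
- Difference: 238 + 21 = 259 days = 259/365.25 = 0.71 years.

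A massage course ending in March 2020 would be compatible with the three-month limit in exclusion 11 for that injection date, so the case is possible in an eligible subject.

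**4. Default branch across the year end.** End date 2020 only, consent 15 Dec 2020, injection 8 Jan 2021 (gap 24 days). The end year is not the injection year, so the default gives 31 Dec 2020. Consent minus that date is -16 days = -0.044 years. The default therefore needs a cap as well.

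**5. With a cap at the day before the Screening Visit** (taking consent to be on the day of that visit).
- Case 2: 23 Nov 2020, +1 day = +0.003 years.
- Case 3: 31 Mar 2020, +0.652 years.
- Case 4: 14 Dec 2020, +1 day = +0.003 years.

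No value is negative.

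**The case against.** The strongest reply has four parts.

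*The exception is narrow.* It does not apply to all partial end dates, only to those whose year is the injection year; others follow the month-end and December defaults. This is right and sets the scope of the point.

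*The overwritten month depends on one reading.* The exception comes directly after the December clause, and its evident purpose is to stop a December imputation from falling after dosing. If it was meant only for missing months, known months survive. That reading is reasonable, so the sentence needs clarifying and the 0.7-year figure is conditional. Year-only dates in the injection year still give negative values.

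*Few subjects are exposed.* Exclusion 11 in Protocol 5.2 bars liposuction, injections, radiofrequency, laser, implants, cryolipolysis, surgery and investigational treatments in the 12 months before dosing, so in an eligible subject these cannot have ended in the injection year. Endermologie and massage carry 6-month and 3-month limits. What remains is mainly creams and home therapies, or Endermologie and massage when dosing is late enough in the year, and only with an incomplete date. This stands.

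*The cap does not recover the truth.* A year-only date capped just before screening still gives a value near zero, so recency remains biased toward zero. This also stands: the cap makes the value possible, not accurate.

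A reader might further infer that dating a prior treatment to Day 1 would create false washout violations or protocol deviations. The documents do not support this. Eligibility is reviewed at screening and again before dosing. SAP 4.3 derives deviations from eCRF data, vendor data and monitoring reports, without mention of imputed dates. The cellulite-treatment deviation rule in SAP 4.5 covers use after the Day 1 visit, and an end date on Day 1 is not after it.

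**Conclusion.** The rule is wrong as written, and the consequence is minor. When the exception applies to a subject's most recent cellulite treatment, time since last treatment is certain to be negative, from -0.003 to -0.077 years, and the imputed date conflicts with the SAP's own definition of a prior treatment. The default branch can also produce a negative value when screening crosses the year end. If the exception is taken literally for dates with a known month, the error can reach about 0.7 years in the example shown.

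The 1-to-28-day range assumes a single screening. Protocol 5.4 allows rescreening, and if the earlier consent date were used for a rescreened subject the negative value would be larger. The range describes the reported value; the error against the true interval can be greater, as the known-month case shows.

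The effect is confined to one descriptive baseline variable in the few subjects with partial dates. No endpoint, analysis population or safety summary uses it, and there is no basis in the documents for extending the concern to washout or deviation findings.

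**What to change.** Replace the end-date sentence in SAP 6.3.1.3 with a rule to this effect:
- If only the day is missing, use the last day of the recorded month.
- If the month is missing, use 31 December of the recorded year.
- Never replace a recorded month.
- If the treatment was reported as prior and the imputed date falls on or after the Screening Visit, set it to the day before that visit, and in no case later than informed consent.

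This removes the injection-year exception, makes the section agree with SAP 4.5, and covers the year-end case. If the sponsor prefers to keep a separate exception, it should state that it applies only when the month is missing, and it should be tied to the Screening Visit or consent, not to the first injection. The cost is one SAP sentence and one line of programming; no data collection changes.

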#### **6.3.1.4. Missing Last Menstrual Date**

Missing date of last menstrual period will be imputed with the last day of the month and missing onset month will be imputed with December.

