#### **Study period:**

Estimated date first subject enrolled: 01 October 2020 Estimated date last subject completed: 01 June 2021

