#### 8.3.1. Medical and Cellulite History

Medical and cellulite history will be obtained at the Screening Visit. Medical history will include a review of the following systems: general, dermatological, respiratory, cardiovascular, gastrointestinal, genitourinary, gynecological, endocrine, musculoskeletal, hematological, neuropsychological, immune (allergies), and head, eyes, ears, nose, and throat. Historical and current medical conditions including date of last menstrual period will be recorded. History of tobacco, alcohol, or illegal drug use (never, current, former) will also be collected.

Surgical history will include a review of all surgical procedures completed in the prior 5 years and any surgery completed at any time in the treatment area.

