The study is expected to enroll subjects over a period of approximately 3 months. Subjects will participate in the study for approximately 29 weeks, including a screening period of up to 28 days. The entire study is expected to require approximately 12 months to complete. However, the duration of the study may be changed due to possible COVID-19 impacts.

Subject will receive at least 3 and up to 6 treatment sessions (both buttocks or both thighs)  
Sub-areas that are treated within each overall treatment area will not be dosed more frequently than every 56 days

aThe investigator has the option to skip the treatment session

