### **3.8. Medical and Cellulite History**

A medical and cellulite history of the subject will be taken during screening. Medical history will include relevant diagnoses and/or procedures/therapies with onset/resolutions dates. Historical and current medical conditions including date of last menstrual period will be recorded. If onset date of medical history is unknown, then whether it occurred within 5 years or more than 5 years ago will be recorded on the electronic case report form (eCRF).

Surgical history will include a review of all surgical procedures completed in the prior 5 years and any surgery completed at any time in the treatment areas.

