## 4.2. Demographics and Baseline Characteristics

Demographics and baseline characteristics include the following parameters:

- Age.
- Height (at Screening).
- Body weight (at Screening).
- BMI in kg/m^2 (at Screening).
- Gender.
- Race.
- Ethnicity.
- Time since last menstrual period.
- CR-PCSS cellulite severity ratings for thigh and buttock at Screening.
- Hexsel CSS Section D (laxity, flaccidity or sagging of skin) scores at Screening.
- Skin category based on Fitzpatrick scale assessment.
- Report of substance use
  - Alcohol use (Never, Current, and Former).
  - Tobacco use (Never, Current, and Former).
  - Illegal Drug use (Never, Current, and Former).

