### **7.3. Demographics and Baseline Characteristics**

Demographics and baseline characteristics will be summarized by treatment regimen and overall using the Safety Population. Age, height (at Screening), body weight (at Screening), BMI in kg/m^2 (at Screening) and time since last menstrual period will be summarized as continuous variables using descriptive statistics.

Gender, race and ethnicity will be summarized as categorical variables using frequency counts and percentages.

Refer to [Table 19](#) for descriptions of age categories.

The following baseline characteristics will be summarized using frequency counts and percentages:

- CR-PCSS cellulite severity ratings for thigh and buttock at screening (mean and SD will also be provided).
- Hexsel CSS Section D (laxity, flaccidity or sagging of skin) scores at screening (mean and SD will also be provided).
- Skin category based on Fitzpatrick scale assessment.
- Report of substance use
  - Alcohol use (Never, Current or Former).
  - Tobacco use (Never, Current or Former).
  - Illegal Drug use (Never, Current or Former).

All demographic and baseline characteristics will be presented in subject listings.

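### The rule for a partly known date of last menstrual period has no upper limit, so it can impute a date after screening and could give a negative time since last menstrual period

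*SAP*

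**What the plan says.** SAP 6.3.1.4 is a single sentence. A missing day becomes the last day of the month, and a "missing onset month will be imputed with December". It names no limit at screening, consent or first injection.

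The date comes from the history. Protocol 8.3.1 states: "Medical and cellulite history will be obtained at the Screening Visit". SAP 3.8 adds: "Historical and current medical conditions including date of last menstrual period will be recorded".

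The imputed date feeds one derived quantity. SAP 4.2 lists "Time since last menstrual period" among the baseline characteristics. SAP 7.3 says that "time since last menstrual period will be summarized as continuous variables using descriptive statistics", by treatment regimen and overall, in the Safety Population. SAP Table 19, which holds the derived-variable definitions, has no row for it, so neither the formula nor the reference date is stated.

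The preceding section, SAP 6.3.1.3, uses the same month-end and December convention for the end dates of earlier cellulite treatments. There it adds an exception: if the end year is the year of injection, the first injection date is used instead. That exception does not extend to the last menstrual period.

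**The concern.** A date taken down at screening cannot lie after screening. Month end and December are the latest dates compatible with what is known, so the rule overshoots whenever the known part coincides with the screening month or year and screening is not itself at the end of that period. For a menstruating woman the last period usually falls in or just before the screening month, so within that group a partial date will often be of the kind that fails.

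What is at stake is the credibility of one row of the baseline table and of the matching listing. SAP 6.1 sets display rules for the minimum and maximum, so a negative minimum could be printed. With about 16 subjects per regimen, one wrong record also moves the mean visibly.

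**Working it through.** The plan states no figure on this point, so there is none to reproduce. The check applies the rule literally.

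**Inputs**
- Rule: SAP 6.3.1.4, as quoted above.
- Calendar: Protocol synopsis, "Estimated date first subject enrolled: 01 October 2020"; SAP 3.1, "The study is expected to enroll subjects over a period of approximately 3 months".
- Longest gap from screening to Day 1: 28 days (Protocol 5.4).
- Reference date: not given in Table 19. Two are assumed in turn, the Screening Visit and Day 1 at the latest permitted 28 days after it.

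**Formula.** Time since last menstrual period = reference date - imputed date.

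**Two cases by hand**
- Screening 15 October 2020, only 2020 known, imputed 31 December 2020: -(16 + 30 + 31) = -77 days.
- Screening 1 October 2020, same known year: -(30 + 30 + 31) = -91 days.

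**Further cases (days)**

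| Screening | Known part | Imputed | Reference: screening | Reference: Day 1 (+28) |
|---|---|---|---|---|
| 1 Oct 2020 | 2020 | 31 Dec 2020 | -91 | -63 |
| 15 Oct 2020 | 2020 | 31 Dec 2020 | -77 | -49 |
| 15 Nov 2020 | 2020 | 31 Dec 2020 | -46 | -18 |
| 15 Dec 2020 | 2020 | 31 Dec 2020 | -16 | +12 |
| 15 Jan 2021 | 2021 | 31 Dec 2021 | -350 | -322 |
| 1 Oct 2020 | Oct 2020 | 31 Oct 2020 | -30 | -2 |
| 10 Nov 2020 | Nov 2020 | 30 Nov 2020 | -20 | +8 |
| 10 Nov 2020 | Oct 2020 | 31 Oct 2020 | +10 | +38 |
| 15 Jan 2021 | 2020 | 31 Dec 2020 | +15 | +43 |
| 15 Oct 2020 | 2019 | 31 Dec 2019 | +289 | +317 |

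The January 2021 rows apply only if screening ran past the planned three months. For a missing day, -30 is the extreme: it needs screening on the 1st of a 31-day month and a period recorded in that same month. The last three rows show that the rule gives no negative value when the known month or year is earlier than that of screening.

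**How often a partial date would fail.** As an illustration, assume screening spread evenly over 1 October to 31 December 2020 and the true date spread evenly over 0 to 27 days before screening.

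| Missing part | Reference: screening | Reference: Day 1 (+28) |
|---|---|---|
| Day only | about 53% negative | about 0.3% negative |
| Month and day | about 99% negative | about 68% negative |

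The year-only figures can be checked directly. With screening as reference, every screening day except 31 December gives a negative value: 91/92 = 99%. With Day 1 as reference, screening must fall before 3 December: 63/92 = 68%. These are shares of partial dates under the assumptions, not predicted shares of subjects. The documents do not say how many dates will be partial.

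**Effect on a mean.** Take one subject whose true value is assumed to be 14 days and who is imputed at -77. The error is 14 - (-77) = 91 days. It lowers the mean of a regimen of 16 by 91/16 = 5.7 days, and the overall mean of 32 by 91/32 = 2.8 days.

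**The case against.** The best case for leaving the rule alone is that it rarely matters.

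- **Scope.** Only partial dates in the screening year or month can fail. A subject who qualifies as postmenopausal under inclusion criterion 4 has had no menstrual flow for 12 months before screening, so her last period lies in an earlier calendar year. The rule then gives 31 December of the previous year at the latest, which precedes screening. A forgotten month is arguably most likely in exactly these women. This stands and limits the reach of the point.
- **Reference date.** The negative values depend on a reference date that the SAP does not give. With Day 1 as reference, most day-missing cases turn positive. This also stands, but many year-only cases remain negative. Under either reference the imputed date itself can still fall after the visit at which it was recorded.
- **Consequence.** The variable is descriptive and enters no efficacy or safety analysis. This stands.

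A reader might go further and infer that the imputed date could affect the 12-month postmenopausal check in inclusion criterion 4. The documents do not support that. The criterion is applied from the subject's history at screening and Day 1 (Protocol 5.1), and no section applies an imputed date to eligibility.

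A reader might also infer that the table is bound to show negative values, or that the mean will fall below zero. Neither follows. The number of partial dates is unknown, and a mean below zero would need many such records.

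**Conclusion.** The rule is wrong as written, and the matter is minor. It is a stated rule that can produce impossible dates, not merely a missing detail, and the limit that SAP 6.3.1.3 adds to the same convention is absent here. The size, from -77 to -91 days for the October year-only examples and at most -30 days for a missing day, rests on screening as the reference date. With Day 1 up to 28 days later, the problem is largely confined to year-only dates. Negative values could appear in one descriptive baseline row and its listing. Efficacy, safety and eligibility are not affected.

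**What to change.** In SAP 6.3.1.4, keep the month-end and December convention but set the imputed date to the earlier of the rule's date and the Screening Visit date. In Table 19, add a row for time since last menstrual period with its formula and reference date.

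With screening as the reference, the cap turns every negative case above into 0 days and leaves the valid ones unchanged (10, 15 and 289 days). With Day 1 as the reference, a capped record equals the gap from screening to Day 1, so it cannot be negative. A capped value is still the shortest interval compatible with the known part of the date, so it too leans towards zero, but it is a possible value.

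The cost is one clause and one table row in the SAP, with a small programming change. No new data and no protocol amendment are needed.
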